4.3.2. Sample Size Re-estimation

Sample size re-estimation is not currently anticipated. The change to the primary endpoint led to the re-estimation of the number of events required but not to the re-estimation of the sample size (Appendix 1, Amendment 2).

4.4. Randomization

Participants willing and eligible to be randomized will be stratified by the following: sex, prior history of CVD (primary vs. secondary prevention cohorts), and statin use at baseline, defined as those who are taking no statin at baseline or are statin intolerant compared to all others. Within each strata, participants will be randomized with equal probability to active K-877 or placebo.

Kowa Research Institute, Inc. Statistical Analysis Plan – Protocol K-877-302 (PROMINENT)

5. Clinical Assessments

The schedule of clinical assessments is as follows:

			Post- Study Safety Call		Within 30D°		X							
			CSED Visite	Withi	n 60D ^b	X							X	X
			V15 (M24), V21 (M36), V27 (M48), V33 (M60)		±2W	3 X							X	X
			V11 (M16), V13 (M20), V17 (M28), V19 (M32), V23 (M40), V25 (M44), V29 (M52), V31 (M56)		±2W	χ¢							X	X
,	Period	V8(M10),	V10 (M14), V12 (M18), V14 (M22), V16 (M26), V20 (M34), V22 (M38), V24 (M42), V26 (M46), V28 (M50), V30 (M54), V31 (M58),		±2W		X							X
	Treatment Period	6	M12		±2W	X							Х	Х
	Ţ	4	W8		±2W	X							Х	Х
		9	9W		±2W	×							×	×
		2	M4		±2W	X							×	X
		4	M2		±2W	X								X
L,		3	2W		±3D		Xe							×
erioda	Random -ization	7	0	3W to	5W from V1	X				x	х	Х	x	×
Run-In P	Retest	1.1		Up to 2W	from V1	X						X		
Placebo Run-In Perioda	Screening/ Enrollment	1	₩£-		Up to 6W from V0	X				X	X	X	Х	X
	Pre- screen	0	M9	Within 6W	prior to V2	X			Х	Х	X	X		
		Visit	Week (W)		Study Visit Window	In-Person Visit	Telephone Visit ^d	Assessment	Informed consent	Demographic Data and Medical History ^f	Medical records submission ^f	Inclusion/exclusion	Cardiovascular risk factors and alcohol use	Concomitant medications

Kowa Research Institute, Inc. Statistical Analysis Plan – Protocol K-877-302 (PROMINENT)

Post- Study Safety Calle			Within 30D°		X											
			CSED Visite	Withi	n 60D ^b	X			ЗX	X		X			X	X
	Period		V15 (M24), V21 (M36), V27 (M48), V33 (M60)		±2W	3 X			вX	X	X	X			X_{l}	X_{l}
			V11 (M16), V13 (M20), V17 (M28), V19 (M32), V23 (M40), V25 (M44), V29 (M52), V31 (M56)		±2W	3 X			вX	X	X	X				
		V8(M10),	V10 (M14), V12 (M18), V14 (M22), V16 (M26), V18 (M30), V20 (M34), V22 (M38), V24 (M42), V26 (M46), V28 (M50), V30 (M54), V31 (M54), V31 (M54), V31 (M54),		±2W		X									
	Treatment Period	6	M12		±2W	X			Xg	Х	X	X			X	X
	Ţ	7	M8		±2W	X				×	Х	Х				
		9	9W		±2W	X				×		Х		x		
		5	M		±2W	X				×	X	Х	×		Х	×
		4	M2		±2W	X									Х	
		3	2W		±3D		Xe									
erioda	Random -ization	2	0	3W to	5W from V1	X			Xg	х	Xi	Х	X	Х		×
Run-In P	Retest	1.1		Up to 2W	from V1	X									X	
Placebo Run-In Perioda	Screening/ Enrollment	1	WE-		Up to 6W from V0	X				X	\mathbf{X}^{i}		X		X	
	Pre- screen	0	89	Within 6W	prior to V2	X										
		Visit	Week (W)		Study Visit Window	In-Person Visit	Telephone Visita	Assessment	EQ-5D-5L Questionnaire ^g	Physical exam/ Vital signs ^h	Dispense study drugi	Compliance check	Blood sample for archival	Non-fasting blood sample ^k	Fasting blood sample ^k	Urine sample

Kowa Research Institute, Inc. Statistical Analysis Plan – Protocol K-877-302 (PROMINENT)

Study Safety Call Within $30D^{c}$ Post-× CSED Visitb Withi $60D_{\rm p}$ = × V27 (M48), V21 (M36), V15 (M24), V33 (M60) ±2W × V13 (M20), V17 (M28), V19 (M32), V23 (M40), V25 (M44), V29 (M52), V11 (M16) V31 (M56) ±2W × V28 (M50), V30 (M54), V10 (M14), V12 (M18), V14 (M22), V16 (M26) V18 (M30) V20 (M34), V22 (M38) V24 (M42) V26 (M46), V32 (M58) V34 (M62) V8(M10). ±2W × Treatment Period **M12** ±2W × $\pm 2W$ **X** × ±2W **M**6 9 × ±2W Σ 4 5 × ±2W M × ±3D 2₹ × Random from V1 -ization 3W to SW. 0 Placebo Run-In Perioda Retest Up to 2W from 7 Enrollment Screening/ from V0 Up to 6W 3W Within creen prior to V2 **≷** Pre-**§** 0 Week (W) Study Visit Window In-Person Visit Visit or Month (M) Telephone Visit^d Assessment

× × × filtration rate; FGF-21= fibroblast growth factor - 21; GGT= gamma glutamyl transpeptidase; HbA1c= Hemoglobin A1c; HF= heart failure; hsCRP= high-sensitivity C-reactive aminotransferase; BMI= body mass index; BUN= blood urea nitrogen; CBC= complete blood count; CK= creatine kinase; CK-18= cytokeratin-18; CSED= Common Study End protein; HCG= human chorionic gonadotropin; HDL-C= high-density lipoprotein cholesterol; IEC= Institutional Ethics Committee; IRB= Institutional Review Board; LDH= Date; CV= cardiovascular; CVD= cardiovascular disease; D=day; EQ-5D-5L= European Quality of Life-5 Dimensions 5 Level Questionnaire; eGFR= estimated glomerular ultracentrifugation; REC= Research Ethics Committee; SAE= serious adverse event; sdLDL-C= small dense low-density lipoprotein cholesterol; TG=triglyceride(s); TSH= lactate dehydrogenase; LDL-C= low-density lipoprotein cholesterol; M=month; NMR= nuclear magnetic resonance; PAD: peripheral artery disease; PUC: preparative × × Abbreviations: Apo= apolipoprotein; AE= adverse event; ALP= alkaline phosphatase; ALT= alanine aminotransferase; ANGPTL= angiopoietin-like; AST= aspartate × × × × × × × thyroid stimulating hormone; T4= thyroxine; W=week; WOCP: Women of child-bearing potential × × × × × × × × × Pregnancy test in Adverse eventsⁿ Efficacy events° $WOCP^{m}$

 \times

A 21-day Placebo Run-In Period (maximum 35 days) begins at the Screening/Enrollment Visit (Visit 1).

b The CSED Visit will be scheduled within a 60-day window after study termination is announced, irrespective of the date that the participants were randomized. Participants will continue study medications through the CSED Visit unless the study is stopped for evidence of increased hazard.

^c The Post-Study Safety call will occur approximately 30 days after the CSED Visit, during which final AEs and post study efficacy events will be collected.

Kowa Research Institute, Inc.

Statistical Analysis Plan – Protocol K-877-302 (PROMINENT)

- d Telephone visits will alternate with in-person visits occurring approximately every 4 months; after Month 10; the Month 6 visit is an in-person visit for non-fasting blood
- e Visit 3 will be a well-being telephone call conducted at Week 2 (±3 days) after the Randomization Visit to provide participant support and reinforce dosing. During this telephone call, SAEs and efficacy endpoints (see footnote o) will be recorded.
- May occur up to Randomization Visit. Medical history/medical record submission includes: qualifying at least 1 TG level is \geq 150 mg/dL (1.69 mmol/L), and at least 1 HDL-C rosuvastatin ≥ 20 mg/day, simvastatin ≥ 40 mg/day, or pitavastatin 4 mg/day); and documentation of statin intolerance (if applicable). See protocol Section 10.1 for details on level is ≤ 45 mg/dL (1.16 mmol/L); qualifying type 2 diabetes diagnosis; qualifying CVD event; evidence of LDL-C ≤ 100 mg/dL (2.59 mmol/L) within 12 months if documented statin intolerant, or LDL-C \le 70 mg/dL (1.81 mmol/L) within 12 months if not on qualifying moderate- to high-intensity statin (atorvastatin \ge 40 mg/day, required evidence and acceptable documentation.
- Self-administered Quality of Life questionnaire will be completed at the Randomization Visit, annually, at the first in-person visit after a study endpoint occurs, and at the CSED
- pressure and heart rate, height (Visit 1 and CSED Visit only), body weight, and waist circumference; the BMI will be calculated. Height will only be measured at Visit 1 and the h The physical examination comprised a brief routine examination of body systems (eg. general appearance, head and neck, chest and lungs, etc.). Vital signs include blood CSED Visit. Vital signs should be collected after the participant has been resting for 5 minutes in a seated position.
 - administration instructions for the Placebo Run-In Period. At the other indicated visits, randomized participants will receive either pemafibrate or placebo according to their At Visit 1 (Screening/Enrollment Visit), only placebo tablets will be dispensed to all enrolled participants for the Placebo Run-In Period (maximum 35 days), along with
- regulations and where approved by the IRB/IEC/REC and regulatory authorities, as applicable; samples will be stored in a biobank at the Brigham and Women's Hospital for Fasting (Visit I and Visit 5) and non-fasting (Visit 2) blood samples for archival will be collected from consenting participants at sites in countries where allowed by local future biomarker studies (all consenting participants) and genetic testing (only participants who consent additionally to genetic testing).
 - ^k Blood samples will be collected for safety and efficacy assessments (See Appendix A in protocol Section 21.1 for details):
- Safety laboratory tests: biochemistry panel (including electrolytes [K, Na, Cl], AST, ALT, GGT, ALP, total bilirubin, direct bilirubin, CK, total protein, LDH, uric acid, creatinine, calculated eGFR, BUN) and hematology (CBC with differential), TSH, and free T4.
- Core and advanced lipid parameters (total cohort): TG, HDL-C, LDL-C (direct and calculated), calculated VLDL-C and non-HDL-C, TC, ApoB, ApoA1, ApoC3, ApoE, directly measured remnant cholesterol; LDL-C by beta quantification (PUC), lipoprotein particles (NMR size, concentrations, and subfractions), HDL-TG and LDL-TG by PUC, and directly measured sdLDL-C and LDL-TG;
- Inflammatory and glycemic parameters (total cohort): fasting glucose, HbA1c, hsCRP, and FGF-21.
- annual in-person visits (ie, Month 24/Visit 15; Month 36/Visit 21; Month 48/Visit 27, and Month 60/V33 as applicable). Effective from global protocol amendment 2, frequency 1 After the first year (Month 12), fasting blood and urine samples will be collected for safety laboratory assessment and for lipid profiles and albumin/creatinine assessments at Expanded exploratory lipid and non-lipid parameters (US/Canada subcohort): ApoA5, ApoB48, ANGPTL3, ANGPTL4, PCSK9 mass, CK-18, and type IV collagen. of these additional blood safety measurements will be reduced to once annually based upon DSMB review of blood safety data. Urine samples need not be fasting but are collected at time points when participants are fasting for other laboratory assessments.
 - m Pregnancy testing will be performed by serum testing (beta-HCG) at all specified time points. Testing need not be fasting but specimens are collected at time points when participants are fasting for other laboratory assessments.
 - SAEs will be collected up to and including the Randomization Visit, with serious and non-serious AEs collected thereafter.
- ^o Primary and secondary efficacy events include: MI, ischemic stroke, coronary revascularization, CV death, total mortality, hospitalization for HF, non-ischemic stroke, diabetic retinopathy, diabetic nephropathy, and PAD (see protocol Section 11.1 and Section 11.2 for definitions of efficacy events)

5. PLANNED ANALYSES

5.1. Data and Safety Monitoring Board (DSMB)

The details regarding the DSMB processes and procedures will be outlined in the DSMB Charter. The DSMB Charter will specify the analyses to be included in the regular reviews of cumulative safety data. The DSMB will also be responsible for assessing whether results from the interim analyses justify stopping the trial early for futility. The analyses planned will be a subset of the analyses described in this SAP for the final analyses.

5.2. Interim Analyses

Three interim analyses will take place for this study. The analysis methodology for the interim analyses will be consistent with the final analysis described in the main body of this SAP. The one difference is that censoring at the interim analysis will utilize the interim analysis data cutoff date instead of the end of study date. The list of outputs provided with the full set of output templates (planned for the final analysis) will highlight which of these outputs will also be provided for the interim analyses.

To preserve alpha and to minimize the likelihood of an inflated effect estimate associated with early stopping, preplanned efficacy analyses will occur at accrual of approximately 50% and 75% of the planned study primary endpoints. The design of the study, including evaluation of the implications of interim monitoring on study power, considered that stopping boundaries would be based on the Haybittle-Peto method. Under this approach, the Z-values for the boundary at the 50% and 75% information times would be ± 3.29 , corresponding to 2-sided p-values of 0.001. Additionally, the DSMB will also consider the direction of effect for each of the components of the primary endpoint as well as the sensitivity analysis for loss-to-follow-up, ensuring that the point estimate for each is consistent with the composite result and there is no concern for safety. The DSMB will also consider the direction of the effect in women, again ensuring consistency with the overall result and no concern for safety. Specifically, in order for the study to be stopped early, the estimated HR for the pemafibrate group compared to placebo must be < 1 for each component of the primary endpoint as well as for the subgroup of women. Further, the HR of 1.36 seen in ACCORD must not be in the 95% CI for the primary endpoint in the subgroup of women.

As a guideline for considering a recommendation to stop the study early because of convincing evidence of inefficacy (futility), preplanned inefficacy bounds will also be considered at accrual of approximately 30%, 50%, and 75% of planned study endpoints. Based upon the Linear 10% Inefficacy Boundary approach described by Freidlin, Korn, and Gray³, the inefficacy boundary will be crossed if the observed relative hazard of the primary endpoint associated with pemafibrate assignment is greater than 1.000 at the first interim futility analysis, greater than 0.996 at the second interim futility analysis, or greater than 0.988 at the third interim futility analysis and the 95% CI excludes the expected effect. Simulations performed by Freidlin et al indicate that their Linear 10% Inefficacy Boundary approach is associated with a less than 1% loss of power due to inefficacy monitoring. Further, their approach is more conservative than a 10% or 30% conditional power approach in later follow-up (ie, after 70% of information is

accrued). However, the Linear 10% Inefficacy Boundary approach is more aggressive than a 10% (or even a 20%) conditional power rule at earlier information accrual points, so a more conservative boundary may be preferred at the first interim futility analysis.

5.3. Final Analyses

This trial is endpoint driven. When the appropriate number of major cardiovascular events have occurred, a close out procedure will be initiated. The close out procedure will end at the date of the last visit of the last patient, which will be the analysis cutoff date. Information will continue to be collected after the final visits, including endpoint adjudication, and follow-up of patients who withdrew consent or did not attend their final visit. Database lock will occur after data cleaning and adjudication of all endpoints.

All final, planned analyses identified in this SAP will be performed by IQVIA Biostatistics following sponsor authorization of this statistical analysis plan, database lock, and unblinding of treatment.

6. GENERAL CONSIDERATIONS FOR DATA ANALYSES AND HANDLING

6.1. General Summary Table and Individual Subject Data Listing Considerations

In general, summary tables will be organized with respect to treatment group (K-877 followed by placebo). When deemed appropriate, tables will display sub-group differences by treatment group.

Summary tables for medications, medical conditions, and adverse events are coded according to standard dictionaries including the WHO Drug standard dictionary and the MedDRA dictionary.

Supportive individual Subject Data Listings, as a minimum, are sorted and presented by treatment group (group) and investigational site (center). Listings will also include subject number, visit number, visit date, and days relative to the initiation of double-blind treatment, if applicable.

6.2. Software Version

Derived data sets will be analyzed and summary data tables generated using SAS version 9.4 or higher.

6.3. Data Presentation Conventions

Continuous variables (eg, age) will be summarized using descriptive statistics (the number of subjects with available data, the mean, standard deviation (SD), median, and minimum and maximum). Categorical variables (eg, race) will be summarized using counts and percentages. Percentages will be calculated using the total subjects per treatment group.

The following conventions are applied to all data presentations and summaries.

- For continuous variables, all mean and median values will be formatted to one more decimal place than the measured value. Standard deviation values will be formatted to two more decimal places than the measured value. Minimum and maximum values will be presented with the same number of decimal places as the measured value.
- For categorical variables, the number and percentage of responses will be presented in the form XX (XX.X%) where the percentage is in the parentheses.
- Date variables will be formatted as DDMMMYYYY for presentation. Time is formatted in military time as HH:MM for presentation.
- Wherever possible, data will be decimal aligned.
- P-values, if applicable, will be presented to 3 decimal places. If the p-value is less than 0.001 then it will be presented as <0.001. If the rounded result is a value of 1.000, it will be displayed as >0.999.
- Unless otherwise stated, any statistical tests performed will use 2-sided tests at the 5% significance level.

6.4. Analysis Populations and Overall Study Period

6.4.1. Screen Failures

Subjects are considered a screen failure if they are not found to be eligible for randomization under the eligibility criteria specified in the protocol. Once they are randomized and receive study drug (even if mis-randomized) they are included in one or more analysis sets below.

6.4.2. Safety Population

The safety population includes all subjects who received at least one dose of study treatment. Subjects will be analyzed according to their randomized treatment group, unless a subject inadvertently receives the incorrect drug during the entire study, in which case, the subject will be grouped according to the treatment actually received.

6.4.3. Intent-To-Treat (ITT) Population

The Intention-To-Treat population will serve as the primary analysis population and will include all randomized subjects who received at least one dose of study treatment. Subjects will be analyzed according to their randomized treatment group regardless of whether they adhere to their assigned treatment.

6.4.4. Per-Protocol (PP) Population

The Per-Protocol population will include all subjects in the ITT analysis set who have been identified by having efficacy affected through violations on the CTMS log or compliance. The reason for exclusion was identified with CTMS external data source and an external compliance data source. Subjects will be analyzed according to their randomized treatment group regardless of whether they adhere to their assigned treatment.

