8.3. Treatment Compliance

At each in-person visit, participants will be reminded by the sites of the importance of adhering to their treatment regimen for the entire duration of the study. Any interruptions of therapy should be as brief as possible and only for clinically-indicated reasons, such as AEs. Study medication can be re-started at any time in participants willing to resume treatment. Discontinuations will be discouraged and should be based on compelling clinical reasons.

For every participant, an assessment of compliance with study drug must be obtained at each scheduled in-person visit where study drug is dispensed and unused study drug returned. Compliance is defined as $\geq 75\%$ for the Placebo Run-In Period and $\geq 80\%$ during the treatment period.

Study medication will be dispensed in amounts exceeding the amount required until the next scheduled study visit. Participants will be instructed to return all unused study medication at the next visit. Compliance to the study drug regimen will be evaluated by tablet count of unused tablets and will be documented in the eCRF. If compliance falls below 80% during the post-randomization period, the investigator or designee will assess potential factors leading to the lack of compliance and counsel the participant. At the end of the study, the final study drug compliance will be calculated by unused tablet count.

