9.5. Study Drug Administration

Participants will self-administer their assigned study drug daily over the course of the study treatment period. Participants will take an oral dose of pemafibrate 0.2 mg or matching placebo tablet twice daily starting the day after completion of Visit 2. Participants may take the study drug in either a fed or fasted state (before or after meals); however, participants should be instructed by the sites to try and remain consistent with the time of dosing for all doses throughout the study. Participants will be instructed by the site to follow dosing instructions on the drug packaging, and to return all remaining unused study drug and packages at the next visit.

Participants will be asked whether there have been any problems with taking the medication, and the investigator will record any significant departure from the dosing instructions (eg, misuse or overdose) as a protocol deviation. For each participant, the number of tablets dispensed, taken, and returned will be recorded on the site's Drug Accountability Log and recorded in the eCRF. Participant compliance will be assessed from information recorded in the eCRF, including study drug count and the start and end date of therapy. Participants will be considered compliant if they have taken $\geq 75\%$ and $\geq 80\%$ of the intended regimen during Placebo Run-In and Treatment Periods, respectively.

Confidential K-877-302 Study Protocol

Version 3 dated 18-Mar-2020

During the active treatment period, if compliance is < 80%, the participant will be counseled by the site on the importance of compliance with the study drug administration.

If a participant has discontinued study drug and the investigator has determined that it is appropriate to re-start study drug, then at the investigator's discretion and with prior approval of either the Sponsor or medical monitor, the investigator may elect to re-start the participant on a once a day dose of study drug with the goal of achieving twice daily dosing.

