To assess the effect of non-informative censoring on the primary outcome, analyses will be performed following the reference-based method outlined by Carpenter, Roger, and Kenward⁶⁹ and detailed in the Statistical Analysis Plan using the piece-wise exponential method described by Lipkovich at al.⁷⁰ For those participants who were lost-to-follow-up, event status after the time of last observation is imputed using the distribution of retrieved dropouts for each arm. Retrieved dropouts are defined as participants who are no longer taking study drug but have agreed to continue to be followed. Other imputation models for missing data will also be explored for their effect on the primary outcome, including models that use the entire placebo group as the reference.

Separate proportional hazards models will also be used to compare the effects of pemafibrate treatment on time to each of the individual components of the composite primary endpoint. Analyses will use methods of competing risks survival analysis and compare the relative effects of randomized treatments on the different components of the composite outcome.^{72, 73} The approach of Lunn and McNeil⁷² provides a readily accessible implementation of a classical approach to competing risk analysis developed by Kalbfleisch and Prentice.⁷⁴

Secondary lipid efficacy endpoints will be analyzed using analysis of covariance (ANCOVA) with a retrieved dropout-based pattern mixture model. Participants with missing data will be imputed using the distribution of retrieved dropouts for each arm, where retrieved dropouts are defined as participants who are no longer taking study drug but have agreed to continue to be followed. Imputed data will be analyzed using an ANCOVA model with baseline measurement as a covariate and the treatment arm and randomization strata as fixed effects.

While all primary analyses are on the ITT population, a Per-Protocol population will also be analyzed which will be limited to participants with no major protocol deviations. Sensitivity analyses for the primary efficacy endpoint will also be conducted examining the effect of compliance and escalation of other lipid-lowering medications. Longitudinal analyses will quantify the impact of pemafibrate on lipid levels, biomarkers of inflammation, and glycemic parameters and other prespecified exploratory lipid and non-lipid biomarkers (Tertiary Endpoints: Section 5.3.1).

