8.4.2. Sensitivity Analyses of the Primary Efficacy Results

Two main types of sensitivity analyses will be done for the primary efficacy results. One sensitivity analysis will be to repeat the primary analysis on the Per-Protocol population. The other includes post-randomization changes in other lipid-lowering therapies.

Sensitivity of the results to post-randomization changes in other lipid-lowering therapies will be assessed using a combination of strategies. As noted in the subgroup analyses, the results will be stratified by baseline statin use. Additionally, an inverse probability treatment weighted approach as developed by Robins and Hernan⁸ will be used to account for time varying changes in lipid-lowering therapy and to obtain an adjusted treatment effect estimate.

Additional analysis to clearly explore the efficacy over time will be performed as follows:

Primary endpoint as well as every component of the primary endpoint will be summarized by treatment and by within year from randomization (first year from randomization, second year from randomization, third year from randomization, fourth year from randomization, and greater than 4 years from randomization).

Secondary endpoints will also by summarized similar to the primary endpoint by within year from randomization.

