8.6. Summary of Reasons for Efficacy Non-Evaluability/Exclusion from Efficacy Analyses

Any subjects excluded from the per-protocol population (PP) will be summarized by treatment group and supported by an individual subject data listing providing the reason each subject was made unevaluable.

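### SAP 6.4.4 defines the Per-Protocol population as the subjects it is meant to leave out

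*SAP*

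**What the plan says.** SAP 6.4.4 is the only place in the SAP that says who belongs to the Per-Protocol population. Its first sentence reads: "The Per-Protocol population will include all subjects in the ITT analysis set who have been identified by having efficacy affected through violations"; the remaining words name the CTMS log and compliance. The second sentence is: "The reason for exclusion was identified with CTMS external data source and an external compliance data source".

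The population is used in SAP 8.4.2: "One sensitivity analysis will be to repeat the primary analysis on the Per-Protocol population". That section calls this one of two main types of sensitivity analysis; the other deals with changes in other lipid-lowering therapy after randomization. SAP 8.6 then asks for a summary by treatment group of the subjects left out of PP, "supported by an individual subject data listing providing the reason each subject was made unevaluable".

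Protocol 14.5 gives its own definition: "a Per-Protocol population will also be analyzed which will be limited to participants with no major protocol deviations". It follows this with: "Sensitivity analyses for the primary efficacy endpoint will also be conducted examining the effect of compliance and escalation of other lipid-lowering medications".

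**The concern.** The first sentence of 6.4.4 states membership in the wrong direction. It admits the subjects whose efficacy data were judged to be compromised and, by implication, leaves out everyone else. A population definition is what the programmers implement. Followed to the letter, the PP sensitivity analysis of the primary endpoint would be run on exactly the subjects it is supposed to remove, and would say nothing about whether the ITT result is robust to deviations.

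A smaller point sits in the same sentence. It brings compliance into PP membership, whereas Protocol 14.5 defines PP by major deviations alone and treats the effect of compliance as a sensitivity analysis of its own. The SAP gives no compliance cut-off for PP, and SAP 8.4.2 does not list the separate compliance analysis.

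**Working it through.** No alpha, power or event count enters this point, so the check is a comparison of texts. Let A be the ITT subjects flagged as having efficacy affected through the CTMS log or compliance.

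| Source | What it implies for PP |
|---|---|
| SAP 6.4.4, first sentence | PP = A |
| SAP 6.4.4, second sentence | The same two sources supply reasons for exclusion, so PP = ITT minus A |
| SAP 8.6 | Subjects outside PP are the unevaluable ones and each has a reason, so PP = ITT minus A |
| Protocol 14.5 | PP = ITT minus subjects with a major deviation |

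**Overlap.** A and ITT minus A are complements, so the literal and intended sets share 0 subjects for any size of A.

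**Consistency with SAP 8.6.** Under the literal rule, the subjects outside PP are those with no flag. SAP 8.6 would then list them as unevaluable with no reason to report. The listing makes sense only under the intended rule.

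**Version gap.** The SAP cover page cites Protocol Version 2, and the protocol supplied is Version 3. The summary of amendments in SAP Appendix 1 records no change to the PP definition. A version difference also could not explain a conflict inside 6.4.4 or between 6.4.4 and 8.6.

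**Why no power or confidence interval is given.** The size of A is not stated. Nor can the design effect be carried over to a PP set: the planned relative rate of 0.834 in Protocol 14.2 already contains 17% non-compliance, since 20% × (1 − 0.17) = 16.6% and 1 − 0.166 = 0.834.

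**Compliance criterion.**
- Protocol 14.5 bases PP on major deviations and names compliance in the following sentence, as a further sensitivity analysis.
- SAP 8.4.2 names PP and lipid-lowering changes, with no separate compliance analysis.
- On the data source, SAP 6.4.4 refers to an external compliance source. Protocol 9.5 says: "Participant compliance will be assessed from information recorded in the eCRF, including study drug count and the start and end date of therapy".
- On the cut-off, Protocol 8.3 and 9.5 define treatment-period compliance as at least 80%. The consequence attached to it is review and counselling ("If compliance falls below 80% during the post-randomization period, the investigator or designee will assess potential factors"), and neither section makes it a rule for PP membership.

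**The case against.** The strongest reply is that nobody would be misled. The next sentence speaks of exclusion, SAP 8.6 calls the excluded subjects unevaluable, and Protocol 14.5 states the right direction. A literal run would produce an absurd 8.6 listing, so the mistake would show itself. PP serves only a sensitivity analysis. On this view it is an editorial slip. It is also only an inference that a negation was dropped; writing include for exclude would give the same sentence.

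Much of this is fair, and it limits the severity. It does not make the sentence correct. SAP section 2 says that the document exists to give details on study populations and that departures from the final plan will be noted in the clinical study report. An analyst who applies the intended rule therefore departs from the written one. The cause of the slip does not matter, because the correction is the same.

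On compliance, several replies carry some weight:
- Protocol 9.5 has significant departures from the dosing instructions recorded as protocol deviations, so some non-adherence may already count, and no passage says that a major deviation cannot be one of compliance.
- The 80% figure is the only treatment-period threshold in the documents.
- The external source might be built from eCRF tablet counts.
- Describing two main types of sensitivity analysis need not be exhaustive, and PP with compliance built in could be read as covering both of the protocol's topics.

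These show that the two documents might be compatible, but the SAP does not say so. Taken alone, the missing cut-off and source would be missing detail rather than error, which is why this point is secondary.

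SAP 7.3 already has subjects and deviation types handed over before database lock and unblinding. That supports the proposed wording on timing for deviations; it does not correct the membership rule.

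**Conclusion.** The concern holds. The membership rule in SAP 6.4.4 is wrong as written and names the complement of the set that the rest of the SAP intends under the same criterion. This rests on the text alone, with no numerical assumption. The effect on the PP estimate cannot be sized, because the number of flagged subjects is not given.

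The consequence is confined to the PP sensitivity analysis of the primary endpoint and the SAP 8.6 listing. The intent is recoverable, so the practical risk is limited. It should nevertheless be fixed, because it is a definite error in an operative definition. The compliance criterion is a lesser matter that needs reconciling with the protocol.

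**What to change.** Replace the first sentence of SAP 6.4.4 with wording such as:

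> *The Per-Protocol population comprises every ITT subject except those identified, before database lock and unblinding, as having a major protocol deviation (CTMS log) or non-compliance that affects efficacy.*

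The sponsor should then settle the compliance criterion against Protocol 14.5 in one of two ways:
- Keep it in PP, state that this adds to the protocol's definition, and give the cut-off and the data source.
- End the exclusion at major protocol deviation (CTMS log), and list the separate compliance sensitivity analysis in SAP 8.4.2.

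SAP 8.6 works as it stands once 6.4.4 is corrected. The cost is one reworded sentence plus one line on compliance, with the cut-off and source if that criterion is kept.
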